9.2. Exclusion Criteria

Clinical Exclusion Criteria:

CE1. Subject has clinical symptoms and/or ECG changes consistent with Acute MI(include STEMI and Non- STEMI) within 1 week

CE2. Subject has cardiogenic shock, hemodynamic instability requiring inotropic or mechanical circulatory support, intractable ventricular arrhythmias, or ongoing intractable angina.

CE3. Subject has received an organ transplant or is on a waiting list for an organ transplant

CE4. Subject is receiving or scheduled to receive chemotherapy within 30 days before or after the index procedure

CE5. Planned PCI (including staged procedures) or CABG after the index procedure

CE6. Subject has a known allergy to contrast (that cannot be adequately pre-medicated)and/or protocol-required concomitant medications (e.g., aspirin or all thienopyridines)

CE7. Subject has one of the following (as assessed prior to the index procedure):

- Other serious medical illness (e.g., cancer, congestive heart failure) with estimated life expectancy of less than 12 months
- Current problems with substance abuse (e.g., alcohol, cocaine, heroin, etc.)
- Planned procedure that may cause non-compliance with the protocol or confound data interpretation

CE8. Subject is receiving chronic (≥ 72 hours) anticoagulation therapy (i.e., heparin, coumadin)

CE9. Subject with out of range complete blood count (CBC) values that are determined by the study physician to be clinically significant.

CE10. Subject has documented or suspected liver disease, including laboratory evidence of hepatitis

CE11. Subject is on dialysis or has baseline serum creatinine level >2.0 mg/dL (177 μ mol/L)

CE12. Subject has a history of bleeding diathesis or coagulopathy or will refuse blood transfusions

CE13. Subject has had a history of cerebrovascular accident (CVA) or transient ischemic attack (TIA) within the past 6 months

CE14. Subject has an active peptic ulcer or active gastrointestinal (GI) bleeding

CE15. Subject has signs or symptoms of active heart failure (i.e., NYHA class IV) or LVEF <

45%at the time of the index procedure

CE16. Subject is participating in another investigational drug or device clinical trial that has not reached its primary endpoint or intends to participate in another investigational drug or device clinical trial within 12 months after the index procedure

CE17. Subject had PCI within the previous 2 weeks

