11.1 Data Collection

Data collection schedule of FAST-CTO China study is summarized in Table 11.1-1.

Table 11.1-1: Data Collection Schedule

	Pre-procedure ≤14 days	Pre- procedure ≤3days	Procedure	Post- procedure /prior to discharge	follow-up and visit		
					Telephone or hospital visit at 30 days (±7 days) ^a	Telephone or hospital visit at 6 months (±30 days) ^a	Telephone or hospital visit at 12 months (±30 days) ^a
Informed Consent Form ^b , including date of signature		X					
Demographic data, including age and gender	X						
Physical assessment, including weight and height	X						
Medical history, including diabetes situation	X						
Angina assessment	X			X	X	X	X
LVEF ^c	X						
12 lead ECG		X		X			
Laboratory detection							
Serum creatinine and urea nitrogen	X						
complete blood count ^d	X						
Pregnancy test ^e	X						
Total CK/CK-MB		X ^f		X ^g			
Troponin ^h		X		X			
Cardiac medication	X	X ⁱ	X ⁱ	X ⁱ	X ⁱ	X ⁱ	X ⁱ
Anticoagulant			X				
Antiplatelet drug		X	X	X	X	X	X
Recent previous PCI procedure information		X					

Table 11.1-1: Data Collection Schedule

	Pre-procedure ≤14 days	Pre- procedure ≤3days	Procedure	Post- procedure /prior to discharge	follow-up and visit		
					Telephone or hospital visit at 30 days (±7 days) ^a	Telephone or hospital visit at 6 months (±30 days) ^a	Telephone or hospital visit at 12 months (±30 days) ^a
Procedure, target lesion, pre-dilation, post-dilation (if applicable) and study stent information			X				
Angiography			X				
AE assessment ^j			X	X	X	X	X
ADE、SAE、SADE、UADE、USADE and device deficiency assessment ^k			X	X	X	X	X

a: All follow-up dates shall be calculated according to the index procedure. However, other protocol required follow-ups may be performed via telephone interview or an office visit within the applicable follow-up window.

b: If the study Informed Consent Form is modified during the course of the trial, study subjects will be re-consented, if necessary.

c: LVEF may be evaluated by angiography, echocardiogram, or radionuclide ventriculography within 60 days prior to enrollment.

d: Differential is only required for subjects who have abnormal leukocyte values.

e: A pregnancy test must be performed within 7 days prior to the index procedure in females of childbearing potential.

f: Preprocedure cardiac enzymes can be drawn from the sheath at the time of sheath insertion.

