11.6 Up to 3 Days Prior to the Index Procedure

The following preprocedural data of all subjects shall be collected within up to 3 days prior to the index procedure:

- Current antiplatelet medication
- Current cardiac medications; collection is only required for subjects with any changes of cardiac medications
- 12 lead Electrocardiogram (ECG)
- Collection of the latest PCI procedure information, including treated vessel, location and procedure type
- Laboratory detection
 - Total CK or CK-MB (if the total CK is $>1\times$ ULN, CK-MB or troponin must be run)
 - Troponin (if CK / CK-MB cannot be run)

It is recommended that the same type of cardiac enzyme shall be collected prior to and after the procedure during the hospitalization (i.e., not converting from CK-MB to troponin, or vice versa).

Note: preprocedural cardiac enzymes can be drawn from the sheath at the time of sheath insertion.

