Lesion Location

Lesion location is the location of the lesion according to the specific coronary artery (i.e., left main, LAD, LCX, or RCA) or bypass graft, and is specified as proximal, mid, or distal. A standard map will be provided to be used for location descriptions.

Leukopenia

Leukopenia is a leukocyte count of $<3.0 \times 10^9/\text{liter}$ for more than 3 days.

Malfunction

A malfunction is a failure of the device to meet performance specifications or otherwise perform as intended.

Myocardial Infarction

The definition of myocardial infarction in FAST-CTO China clinical trial:

Spontaneous myocardial infarction²⁵ (> 72 hours post procedure):

Detection of rise and/or fall of cardiac biomarkers (CK-MB or troponin) with at least one value above the 99th percentile of the upper reference limit (URL) together with evidence of myocardial ischemia with at least one of the following:

- Symptoms of ischemia;
- ECG changes indicative of new ischemia (new ST-T changes or new left bundle branch block [LBBB]);
- Development of pathological Q waves in the ECG;
- Imaging evidence of new loss of viable myocardium or new regional wall motion abnormality.

Percutaneous Coronary Intervention (PCI) and Coronary Artery Bypass Graft (CABG) related Myocardial infarction ²⁶ (≤ 72 hours post procedure)

1. CK-MB in patients with normal baseline concentration reaches any of the following criteria:

- An increase in CK-MB peak to $\geq 10X$ URL during the first 48 hours following the procedure
- An increase in CK-MB peak to $\geq 5X$ URL during the first 48 hours following the procedure, plus new pathological Q-wave in at least 2 contiguous leads, or new persistent LBBB

Or meets any of the following criteria if CK-MB levels are unavailable and baseline troponin concentrations are normal:

- An increase of troponin (I or T) to $\geq 70X$ URL during the first 48 hours following PCI
- An increase of troponin (I or T) to $\geq 35X$ URL during the first 48 hours following PCI, and development of new pathological Q-wave in at least 2 contiguous leads or new persistent LBBB

2. In patient with elevated baseline CK-MB (or troponin) in whom the biomarker levels have shown the tendency to be stable or decrease, if the CK-MB (or troponin) rises by an absolute increment equal to those levels recommended above from the most recent pre-procedure level.

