3. In patient with elevated baseline CK-MB (or troponin) in whom the biomarker levels have not shown to be stable or decrease, if the CK-MB (or troponin) rises by an absolute increment equal to those levels recommended above from the most recent pre-procedure level, plus new ST-segment elevation or depression and clinical symptoms related to myocardial infarction, such as new or aggravated heart failure or persistent hypotension.

New York Heart Association classification

- Class I: Patients with no limitation of activities; they suffer no symptoms from ordinary activities
- Class II: Patients with slight, mild limitation of activity; they are comfortable with rest or with mild exertion
- Class III: Patients with marked limitation of activity; they are comfortable at rest
- Class IV: Patients who should be at complete rest, confined to bed or chair; any physical activity brings on discomfort and symptoms occur at rest

Perforation

Perforations are classified as follows:

- Angiographic perforation: Perforation detected by clinical site or Angiographic Core Laboratory at any point during the procedure.

- Clinical perforation: Perforation requiring additional treatment, including efforts to seal the perforation or pericardial drainage, or resulting in significant pericardial effusion, abrupt closure, MI, or death.
- Pericardial hemorrhage/tamponade: Perforation causing tamponade.

Prolonged Angina Pectoris

Prolonged angina pectoris is angina lasting longer than 1 hour.

Pseudoaneurysm

A pseudoaneurysm is an encapsulated hematoma in communication with an artery. It is often difficult to distinguish from an expanding hematoma at the site of arterial puncture. It usually requires surgical repair.

Randomization

Randomization is the procedure by which subjects are assigned to a treatment group based on appropriate theories of probability including those involving random chance and conditional assignments.

Reference Diameter of Normal Arterial Segment

Reference diameter of the normal artery segment is an angiographic measurement of the artery proximal and/or distal to the lesion intended for angioplasty. This is also referred to as “reference vessel diameter” (RVD).

Repeated Intervention

Repeat intervention is a PCI or CABG performed after the end of the index procedure. The repeat intervention should be performed to improve blood flow.

Restenosis Lesion

A restenosed lesion is a previously treated lesion that again has a stenosis.

Restenosis

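### The baseline sampling rules do not guarantee the CK-MB or troponin level, or the same-marker increment, that the periprocedural (≤72 h) MI criteria require

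*Protocol*

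**What the plan says.** **Definition.** Protocol section 7.1 makes 30-day MACE a primary endpoint and refers to section 31.2 for MI. For the first 72 hours, section 31.2 gives three items:

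- Item 1 applies when the baseline CK-MB is normal, or the baseline troponin is normal and CK-MB is unavailable. CK-MB must reach 10× URL, or 5× URL with new Q waves or persistent LBBB. The troponin thresholds are 70× and 35×.
- Item 2 applies to a raised baseline "in whom the biomarker levels have shown the tendency to be stable or decrease". It needs an absolute rise of the same size from the latest pre-procedure level.
- Item 3 applies to a raised baseline "in whom the biomarker levels have not shown to be stable or decrease". It needs the same rise plus new ST change and clinical symptoms.

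**Baseline sampling.** Section 11.6 asks, within 3 days before the procedure, for "Total CK or CK-MB (if the total CK is" above 1× "ULN, CK-MB or troponin must be run"). The fallback is "Troponin (if CK / CK-MB cannot be run"). Footnote f of Table 11.1-1 adds: "Preprocedure cardiac enzymes can be drawn from the sheath at the time of sheath insertion". No serial sampling is required. On consistency: "It is recommended that the same type of cardiac enzyme shall be collected prior to and after the procedure". Section 11.8 repeats this as a recommendation.

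**Post-procedure sampling.** At least one total CK or CK-MB is due within 1 day. If total CK is abnormal, footnote g allows either CK-MB or troponin as the follow-on test, while section 11.8 names only CK-MB.

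**Other relevant text.** The endpoint text in Protocol section 12 describes MI by total CK above twice the upper limit with a positive MB result and sets no baseline condition. SAP section 7.3 imputes nothing beyond adverse event onset dates.

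**The concern.** Every MI criterion at 72 hours or less is conditioned on a pre-procedure CK-MB or troponin, and items 2 and 3 also need a difference measured in one marker. Three features of the sampling rules leave these inputs unsecured:

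- **Level.** A subject with a normal baseline total CK has met section 11.6 with neither marker measured. If total CK is abnormal afterwards, section 11.8 produces a CK-MB with no baseline.
- **Increment.** A subject with a raised baseline total CK may have troponin before (section 11.6) and CK-MB after (section 11.8). No difference can be taken across two assays.
- **Trend.** Nothing requires the second pre-procedure value that would show stability or a fall, which is what separates item 2 from item 3.

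The accuracy of the reported primary safety rate is at stake. Raised baselines are enrollable: CI4 admits subjects with MI, CE1 excludes only a subject who "Subject has clinical symptoms and/or ECG changes consistent with Acute MI(include STEMI and Non- STEMI) within 1 week", and no criterion sets a biomarker limit. An unmeasured baseline cannot be recovered later by adjudication or analysis.

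**Working it through.** **1. Marker patterns the minimum rules permit.** Each side has five routes: normal total CK only; CK-MB as follow-on test; troponin as follow-on test; CK-MB drawn directly; troponin as fallback. This uses footnote g after the procedure.

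| Baseline | Post: normal total CK only (1 route) | Post: CK-MB (2 routes) | Post: troponin (2 routes) |
|---|---|---|---|
| Normal total CK only (1 route) | 1, no marker | 2, unmatched | 2, unmatched |
| CK-MB (2 routes) | 2, no marker | 4, matched | 4, unmatched |
| Troponin (2 routes) | 2, no marker | 4, unmatched | 4, matched |

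Matched: 4 + 4 = 8. Post-procedure marker without a same-marker baseline: 2 + 2 + 4 + 4 = 12, of which 4 have only a normal total CK before. No post-procedure CK-MB or troponin: 1 + 2 + 2 = 5. Total 25.

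Under section 11.8 (follow-on CK-MB only) the troponin column has one route: 4 + 2 = 6 matched, 2 + 1 + 4 + 2 = 9 unmatched, 5 with no marker, total 20. No pattern guarantees two baseline values.

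**2. When the missing baseline changes the answer.** Let P be the post-procedure CK-MB peak and b a raised baseline, both in multiples of URL (b is an assumption).

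- P < 5: then P − b < 5 as well, so no item is met at any baseline.
- Item 1 needs P ≥ 10 and item 2 needs P − b ≥ 10. They differ for 10 ≤ P < 10 + b, or 5 ≤ P < 5 + b with new Q waves or LBBB. For b = 2 the bands are 10 to 12 and 5 to 7.
- Items 2 and 3 share the increment and differ when ST change or symptoms are absent. With b = 2 and P = 14 the rise is 12: an MI under item 2, and not under item 3 in an asymptomatic subject.
- Items 1 and 3 differ for any P ≥ 10 without the ST change and symptoms. Where the level is missing and a single raised value would fall into item 3, the ambiguity is not confined to the narrow band.

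**3. Weight of the component.** The 30-day MACE table in Protocol section 4.3.3.3 reproduces: 7/147 = 4.8%, non-Q-wave MI 6/147 = 4.1%, and 6/143 = 4.2% after dropping 147 − 143 = 4 subjects with inadequate blood draws. With 2 cardiac deaths, 2 + 6 = 8 events fell on 7 subjects, so one subject had both and 7 − 2 = 5 counted through MI alone.

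**4. Scale at n = 100.** If that rate carried over, 100 × 6/147 = 4.1 MIs would be expected, which caps the affected events at a handful. For the trend problem alone, assuming 5 to 15 subjects with a raised baseline, 5 × 6/147 = 0.2 to 15 × 6/147 = 0.6 MIs. Exact 95% intervals:

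| MACE | Rate | 95% CI |
|---|---|---|
| 3 | 3% | 0.6 to 8.5 |
| 5 | 5% | 1.6 to 11.3 |
| 6 | 6% | 2.2 to 12.6 |
| 7 | 7% | 2.9 to 13.9 |

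**The case against.** The plan permits CK-MB at baseline, requires CK-MB or troponin when total CK is raised, and falls back on troponin when CK and CK-MB cannot be run. Many subjects will have a usable level. A subject left with only a normal total CK could reasonably be presumed to have a normal baseline. Section 11.6 sets a window and no cap on draws, so a single sample is only the minimum. CE1, CE2 (instability, intractable angina) and CE17 (PCI within 2 weeks) all limit raised baselines. An independent Clinical Events Committee adjudicates MI under a charter that is not among these documents. There is no hypothesis or success threshold, so no formal decision turns on one or two events.

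Most of this stands, and it limits the size of the problem. It does not close the gap: the presumption of a normal baseline is written nowhere in these documents, and a committee cannot adjudicate an increment from a value that was never measured.

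Two stronger readings should be set aside. A reader might infer that the MI part of 30-day MACE cannot be classified at all. The documents do not support that: MI after 72 hours has no baseline condition, and CK-MB below 5× URL is a non-event under every item. A reader might also infer that one raised value leaves the governing item undeterminable. Item 3 is worded as the residual class, and stability has not been shown by a single value, so literally it falls there. The plan does not say that this stricter outcome is intended.

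**Conclusion.** The concern holds in limited form. The baseline rules do not guarantee the level or same-marker increment on which items 1 to 3 depend, nor the second value needed to reach item 2. Some periprocedural MIs in the primary safety endpoint therefore cannot be classified as defined even with full compliance.

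The number of subjects is not given and is probably small. The 5 to 15% share is an assumption, and the earlier trial's MI rate may not transfer because section 4.3.3.3 does not state the MI threshold behind it. The effect would be on the accuracy of a descriptive rate, by one percentage point for each subject reclassified on MI alone. It merits correction because MI was the sole route to MACE in 5 of 7 subjects in the earlier trial and the remedy is cheap. Classification also depends on which MI definition governs, since sections 12 and 31.2 disagree.

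**What to change.** 1. In sections 11.6 and 11.8 and Table 11.1-1, require CK-MB for every subject on the baseline sample already drawn, with troponin only where CK-MB is unavailable. Make the same marker before and after a requirement.
2. Reconcile footnote g (CK-MB or troponin) with section 11.8 (CK-MB only).
3. Where an earlier sample within the 3-day window is above the URL, also take the sheath sample that footnote f already allows, as a second baseline point.
4. In section 31.2, state that a single raised value is classified under item 3, as literally worded. In the SAP, report the count under item 2 as a sensitivity analysis.
5. Reconcile the MI wording in Protocol section 12 with section 31.2.

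The cost is one extra assay on existing blood, an occasional extra tube from the sheath, and wording changes. The MI count may differ slightly. These changes secure the baseline only: one post-procedure draw within 1 day still may not capture the 48-hour peak that item 1 refers to.

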4.1.4 Safety

During the study, there was no acute adverse event. Retrospective follow-up was performed on 31 subjects 30 days after the procedure. In these 31 subjects, 3 (9.7%) experienced the adverse event within 30 days post procedure. Two subjects with an unsuccessful procedure had the angina again with slight myocardial enzymes elevation, and they received the CABG procedure subsequently. One subject had the angina again with slight (2x) troponin elevation after the procedure, but he did not receive a further treatment.

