4.2.4 Safety Results

This study assessed relevant complications within 30 days after the procedure for BridgePoint Medical CTO System. Acute complications related to devices include:

- Perforation with hemopericardium or pericardial tamponade. AMI caused by CrossBoss and Stingray devices. AMI is defined as remarkable CPK elevation (> 3 times of the upper limit with positive MB results) and troponin level between 0.02 to 0.10 microg/L.
- MACE(including cardiogenic death, AMI related to lesions and emergent bypass procedure related to treatment segment) events.

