7.1 Primary Study Endpoint

- Technical Success: the ability of the BridgePoint Medical System to successfully facilitate placement of a guidewire beyond a CTO lesion in the true vessel lumen/within the collaterals
- 30-day MACE rate for CTO cases in which the BridgePoint Medical System was used

MACE is defined as the composite of cardiac death, Q-wave and non-Q-wave myocardial infarction, and any ischemia-driven target lesion revascularization. (for MI definition please refer to section 31.2)

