- Type C: Dissection protruding outside the lumen of the vessel persisting after passage of the contrast material
- Type D: Spiral shaped filling defect with or without delayed run-off of the contrast material in the antegrade flow

- Type E: Persistent luminal filling defect with delayed run-off of the contrast material in the distal lumen
- Type F: Filling defect accompanied by total coronary occlusion

Diabetes

Subjects will be categorized as having diabetes mellitus if medical treatment (oral or injection) is required for control of blood glucose levels.

Distal Embolization

Distal embolization is migration of a filling defect or thrombus to distally occlude the target vessel or one of its branches.

Emergency Bypass Surgery

Emergency bypass surgery is CABG surgery performed on an urgent or emergent basis for severe vessel dissection or closure, or treatment failure resulting in new ischemia.

Epicardial Vessel

Epicardial vessels include the LAD and its branches, the LCX and its branches, and the RCA and its branches.

Hypertension

Hypertension is persistently high arterial blood pressure. Various criteria for its threshold have been suggested, ranging from 140 mmHg systolic and 90 mmHg diastolic to as high as 220 mmHg systolic and 110 mmHg diastolic. Hypertension may have no known cause or be associated with other primary diseases.

Hypotension

Sustained hypotension is a systolic blood pressure less than 80 mmHg lasting more than 30 minutes or requiring intervention (e.g., pacing, IABP, intravenous vasopressors, to sustain systolic blood pressure). This excludes transient hypotension or vagal reactions, which are self-limited or readily reversible.

Index Procedure Start Time

Index procedure start time is defined as the time of guide catheter placement.

Index Procedure End Time

Index procedure end time is defined as the time the guide catheter is removed after the final angiography.

Intimal Flap

An intimal flap is an extension of the vessel wall into the arterial lumen.

Late Loss

Late loss is the postprocedure MLD minus the follow-up MLD as determined by QCA.

Left Main Coronary Artery Disease

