
Target lesion failure is any ischemia-driven revascularization of the target lesion, MI (Q-wave and non-Q-wave) related to the target vessel, or (cardiac) death. For the purposes of this protocol, if it cannot be determined with certainty whether the MI was related to the target vessel, it will be considered a TLF.

Target Lesion Revascularization (TLR)

Target lesion revascularization is any ischemia-driven repeat percutaneous intervention, to improve blood flow, of the successfully treated target lesion or bypass surgery of the target vessel with a graft distally to the successfully treated target lesion. A TLR will be considered as ischemia-driven if the target lesion diameter stenosis is $\geq 50\%$ by QCA and there is presence of clinical or functional ischemia which cannot be explained by other coronary or graft lesions. Clinical or functional ischemia is any of the following:

- The subject has a positive functional study corresponding to the area served by the target lesion.
- The subject has ischemic ECG changes at rest in a distribution consistent with the target vessel.
- The subject has ischemic symptoms referable to the target lesion.

A TLR will be considered as ischemia-driven if the lesion diameter stenosis is $\geq 70\%$ by QCA even in the absence of clinical or functional ischemia.

Target vessel

The target vessel is any coronary vessel (*e.g.*, left main coronary artery, LAD, LCX, or RCA) containing a target lesion. Side branches of a target vessel such as the LAD are also considered part of the target vessel.

Target vessel failure (TVF)

Target vessel failure is any ischemia-driven revascularization of the target vessel, MI (Q-wave and non-Q-wave) related to the target vessel or (cardiac) death related to the target vessel. For the

purposes of this protocol, if it cannot be determined with certainty whether the MI was related to the target vessel, it will be considered a TVF.

Target Vessel Revascularization (TVR)

Target vessel revascularization is defined as a TLR (see definition above) or a TVR remote (see definition below).

Target Vessel Revascularization Remote

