Target vessel revascularization remote is any ischemia-driven repeat percutaneous intervention, to improve blood flow, or bypass surgery of not previously existing lesions diameter stenosis $\geq 50\%$ by QCA in the target vessel, excluding the target lesion. A TVR will be considered ischemia-driven if the target vessel diameter stenosis is $\geq 50\%$ by QCA and any of the following are present:

- The subject has a positive functional study corresponding to the area served by the target vessel.
- The subject has ischemic ECG changes at rest in a distribution consistent with the target vessel.
- The subject has ischemic symptoms referable to the target vessel.

A TVR will also be considered as ischemia-driven if the lesion diameter stenosis is $\geq 70\%$ even in the absence of clinical or functional ischemia.

Technical Success

Technical success is the ability of the BridgePoint Medical System to successfully facilitate placement of a guidewire beyond a CTO lesion in the true vessel lumen/within the collaterals in those cases that were otherwise refractory to treatment with a currently marketed guidewire.

Thrombus (angiography)

Thrombus (angiographic) is discrete, mobile intraluminal filling with defined borders with/without associated contrast straining, classified as either absent or present.

Thrombolysis in the Classification of Myocardial Infarction

- TIMI 0: No perfusion.
- TIMI 1: Penetration with minimal perfusion. Contrast fails to opacify the entire bed distal to the stenosis of the duration of the cine run.
- TIMI 2: Partial perfusion. Contrast opacifies the entire coronary bed distal to the stenosis. However, the rate of entry and/or clearance is slower in the coronary bed distal to the obstruction than in comparable areas not perfused by the dilated vessel.
- TIMI 3: Complete perfusion. Filling and clearance of contrast equally rapid in the coronary bed distal to stenosis as in other coronary beds.

Total Occlusion

A total occlusion is a lesion with no flow (i.e., TIMI flow 0).

Transient Ischemic Attack

A TIA is a focal ischemic neurological deficit of abrupt onset and of presumed vascular etiology that resolves completely within 24 hours of onset.

Unanticipated Adverse Device Effect (*Reference: 21CFR Part 812*)

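### A non-fatal emergency bypass or ischaemia-driven revascularisation of a target lesion left untreated after a failed crossing does not itself count in 30-day MACE

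*Protocol*

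**What the plan says.** Protocol Section 7.1 sets the primary safety endpoint: "MACE is defined as the composite of cardiac death, Q-wave and non-Q-wave myocardial infarction, and any ischemia-driven target lesion revascularization". SAP Section 3.1 gives the same composite, but then breaks it down with target vessel revascularisation as the third component.

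The working definitions are in Protocol Section 31.2:

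- **TLR** is ischaemia-driven repeat percutaneous intervention "of the successfully treated target lesion or bypass surgery of the target vessel with a graft distally to the successfully treated target lesion". The success condition attaches to both limbs, and nothing in the protocol or SAP says what successful treatment means.
- **TVR**: "Target vessel revascularization is defined as a TLR (see definition above) or a TVR remote". The remote class covers lesions that did not previously exist, "in the target vessel, excluding the target lesion".
- **Emergency bypass surgery** covers severe dissection or closure, "or treatment failure resulting in new ischemia". It is defined but appears in no endpoint.
- **CEC events** are TVR, MI and death. Section 27.3 names the same three for the event dossier.

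Enrolment happens when a BridgePoint device enters the body (Protocol Section 10.1). The safety analysis takes every enrolled subject in whom any component was used (Protocol Section 11.3.1, SAP Section 4.1), so failed crossings are in the denominator.

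The earlier trials described in the protocol handled bypass differently. The EU trial's MACE included "emergent bypass procedure related to treatment segment" (Section 4.2.4). FAST-CTO gave emergency CABG its own row in its 30-day MACE table (Section 4.3.3.3).

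**The concern.** Section 7.1 reads as inclusive: "and any ischemia-driven target lesion revascularization". The definition that the CEC and programmers would apply is narrower. A subject whose lesion was never opened cannot have a TLR, yet is counted in the denominator of the rate.

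Failed crossings have been exposed to the device without the benefit of an open vessel, so an urgent revascularisation in that group is of direct safety interest. The first-in-man report shows that bypass after failure does happen: "Two subjects with an unsuccessful procedure had the angina again with slight myocardial enzymes elevation, and they received the CABG procedure subsequently" (Section 4.1.4).

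At stake is a primary safety rate, and the 6- and 12-month rates built on the same composite, that leave out one kind of event in one group of subjects. A reader who sets the result beside the EU trial might not notice the difference in definition.

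**Working it through.** **1. Where each event falls under Section 31.2**

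| Event after the index procedure | TLR? | TVR remote? | Counts in 30-day MACE? |
|---|---|---|---|
| Ischaemia-driven repeat PCI or bypass, lesion successfully treated | Yes | No | Yes |
| Same, lesion opened with another CTO device after BridgePoint failed | Unclear: term undefined | No | Unclear |
| PCI of a target lesion left untreated | No | No: target lesion excluded | Only through MI or cardiac death |
| Bypass for a target lesion left untreated, including emergency bypass for treatment failure | No | No: lesion already existed and is the target lesion | Only through MI or cardiac death |
| Ischaemia-driven treatment of a new lesion elsewhere in the target vessel | No | Yes | Only if the TVR wording in SAP 3.1 governs |

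Reading the SAP's third component as TVR does not help the third and fourth rows, because TVR is only the sum of TLR and TVR remote.

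The second row arises because Section 11.7 bars other CTO devices only before BridgePoint failure. The MI route is the periprocedural and spontaneous MI definition in Section 31.2. The cardiac death route includes death from bypass surgery as a procedural complication.

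**2. Reported figures reproduced**

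The plan states no expected MACE rate and no derivation of N = 100, so there is no design figure to reproduce. The background figures reproduce: FAST-CTO MACE is 7/147 = 4.8%, and P(X ≤ 7 | n = 147, p = 0.14) = 0.00025 against the stated 0.0003.

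**3. Failure rates in the earlier studies**

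- First-in-man (Section 4.1.3): 7/44 = 15.9%
- FAST-CTO, by subject (Section 4.3.3.4): (147 − 113)/147 = 34/147 = 23.1%
- EU trial (Section 4.2.5.2): (42 − 28)/42 = 14/42 = 33.3%

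**4. Emergency bypass among those failures**

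The EU trial's only two MACE events were non-Q-wave MIs (Section 4.2.5.3), so no emergent bypass was counted in a composite that included it. FAST-CTO reports 0/147. Failures at risk: 14 + 34 = 48, with 0 events.

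Exact two-sided 95% upper limit: 1 − 0.025^(1/48) = 7.4%. For 23 failures per 100 subjects, 23 × 0.074 = 1.7 events.

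**5. Events left out per 100 subjects**

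Events = 100 × f × q, where f is the failure rate and q is the share of failures with such an event by day 30 and no qualifying MI or cardiac death. The documents do not give q. The 2%, 5% and 10% rows are assumptions, and 7.4% is the limit from step 4.

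| q | f = 15.9% | f = 23.1% | f = 33.3% |
|---|---|---|---|
| 0% | 0 | 0 | 0 |
| 2% | 0.3 | 0.5 | 0.7 |
| 5% | 0.8 | 1.2 | 1.7 |
| 7.4% | 1.2 | 1.7 | 2.5 |
| 10% | 1.6 | 2.3 | 3.3 |

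**6. Effect on a reported rate**

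As an illustration, 5/100 has an exact 95% CI of 1.6% to 11.3%. Adding two omitted events gives 7/100, with a CI of 2.9% to 13.9%.

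**The case against.** The restriction has a rationale. TLR ordinarily means a repeat procedure on a treated lesion. An uncrossed CTO has TIMI 0 flow, so it always meets the 70% stenosis rule in Section 31.2, which needs no ischaemia. Deleting the success condition would turn every elective re-attempt or surgical referral into a MACE event. Nor would the word unplanned screen these out: exclusion CE5 already removes planned PCI or CABG, so any later procedure was unplanned at entry. Failure to open the vessel is captured by technical and procedural success. This stands, and it is why the primary composite should not be rewritten.

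A reader might infer that failed-crossing subjects can never count in MACE. The documents do not support that. A qualifying MI or cardiac death still counts, and a lesion rescued with another device may regain TLR eligibility. The strength of the MI route depends on a threshold that itself needs reconciling: Section 12 gives total CK above twice the upper limit with positive MB, while Section 31.2 starts at five to ten times the reference limit for CK-MB.

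A reader might also divide the two first-in-man bypasses by the seven failures, get 2/7 = 29%, and project 23 × 2/7 = 6.6 omitted events per 100. Section 4.1.4 does not support this as a 30-day rate. It dates the adverse events within 30 days but not the operations, does not call them emergency surgery, and followed only 31 of 44 subjects. It does not say how many of the seven failures were among the 31.

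The borrowed failure rates may be high for this trial. FAST-CTO enrolled refractory lesions and the EU trial defined its technical success in refractory cases, with mean lengths of 32.3 and 36.0 mm. Here lesions must be under 40 mm, without moderate to severe calcification or excessive tortuosity.

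Finally, such surgery would normally be reported as a serious adverse event and tabulated under SAP Section 5.4. That helps only in part: those tables are by system organ class and preferred term, and give no adjudicated revascularisation rate.

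**Conclusion.** The gap is real on the text. A non-fatal emergency bypass, or a clinically ischaemia-driven revascularisation, of a target lesion left untreated after a failed crossing is neither TLR nor TVR, is not named for CEC adjudication, and does not itself enter 30-day MACE.

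The size is uncertain and probably small. For emergency bypass, the two earlier trials that reported it are compatible with anything from none to about 1.7 events per 23 failures. That limit assumes their failures resemble those in this trial. It does not bound non-emergency revascularisation driven by clinical ischaemia, for which the documents give no rate.

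There is no hypothesis test or threshold (Protocol Section 11.2), so no decision rule is affected. The consequence is a descriptive safety rate that may read slightly low, and one that differs from the EU trial's in how bypass is treated. The EU composite had no TLR component, so the two would not be fully comparable in any case.

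**What to change.** Keep primary MACE unchanged, and make three additions:

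1. **Define successful treatment** in Protocol Section 31.2, stating whether a lesion opened with another device after BridgePoint failure qualifies.
2. **Reconcile SAP Section 3.1**, which defines MACE with TLR but tabulates TVR.
3. **Pre-specify a supportive MACE** at 30 days, 6 months and 12 months, adjudicated by the CEC. It adds to the primary components (a) emergency bypass surgery as already defined in Section 31.2, and (b) any target-lesion PCI or CABG after a failed index attempt that meets the clinical or functional ischaemia criteria listed under TLR. The 70% stenosis rule alone should not suffice. List elective re-attempts and elective surgical referrals separately, so that they do not count as safety events.

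The cost is wording in Section 31.2, SAP Section 3.1 and the CEC charter, and a little more adjudication. Adverse events are already collected to 12 months. The supportive rate may come out slightly higher than the primary one.
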